5.5 Criteria for Subject Withdrawal

5.5.1 Criteria for Withdrawal from Study Drug due to Therapeutic Failure

Subjects may continue avelumab treatment beyond radiological disease progression in the absence of significant clinical deterioration and, if in the opinion of the Investigator, the subject will benefit from continued treatment.

Before stopping the treatment with avelumab, progressive disease (PD) should be confirmed by imaging, preferably 6 weeks (but no later) after progression has been diagnosed according to RECIST 1.1.

If progression is based on the occurrence of a new lesion in an area not scanned at baseline, a further on-trial scan 6 weeks later should be performed. Treatment during the confirmation period should continue as scheduled, despite a first observation of progression (according to RECIST 1.1), until confirmation has been made, and further if there is no significant clinical deterioration defined as:

- there are no new symptoms or worsening of existing symptoms,
- there is no change in ECOG PS to ≥ 3 that lasts more than 14 days, or
- the Investigator does not consider it necessary to administer a salvage therapy.

If disease progression is due to brain metastasis, subjects may continue avelumab treatment after the local treatment of the brain lesions provided the above criteria are met in addition to the following and in consultation with the Medical Monitor:

- Brain metastases have been treated locally and are clinically stable for at least 2 weeks prior to re-initiation of treatment with avelumab
- There are no ongoing neurological symptoms that are related to the brain localization of the disease (sequelae that are a consequence of the treatment of the brain metastases are acceptable)
- Subjects must be either off steroids or on a stable or decreasing dose of ≤ 10 mg daily prednisone (or equivalent).

In addition, if disease progression is mainly due to a metastatic lesion (nodal or visceral) that in the opinion of the Investigator may be surgically removed or treated with palliative radiation therapy, subjects may continue avelumab treatment after the local treatment of such a lesion provided that:

- It has been at least 2 weeks (post minor surgery) or 4 weeks (post major surgery) and the subject has fully recovered from the surgery
- It has been at least 2 weeks since the subject's last dose of radiation therapy and any toxicity related to the radiation therapy is recovered to Grade < 2

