7.6.3 ADA Analysis

For Part A: The blood sample for baseline ADA analysis will be collected before trial treatment start. Further serum samples for ADA analysis will be collected within 2 hours before infusion on Days 15, 29, 43 (every 2 weeks) and then every 6 weeks thereafter while on treatment and at the End-of-Treatment visit. Samples positive for ADAs will be re-analyzed to determine the titer.

For Part B: The blood sample for baseline ADA analysis will be collected before trial treatment start. Further serum samples for ADA analysis will be collected within 2 hours before infusion through Week 7, every 6 weeks through Week 25, then at 12-week intervals thereafter while on treatment, and at the End-of-Treatment visit. Samples positive for ADAs will be re-analyzed to determine the titer.

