16.2.2 Progression Free Survival (IERC)

The PFS time, according to the RECIST 1.1, will be defined as time from first administration of trial treatment until first observation of PD or death when death occurs within 12 weeks of the last tumor assessment or first administration of trial treatment (whichever is later). Details on determination of the first disease progression date are specified in the IERC charter.

Specific censoring rules are defined in Table 3 and Table 4. Last adequate tumor assessment is defined as the last tumor assessment result that is not “NE” or “NA”.

PFS time (in months) is defined as:

(date of PD or death - date of the first dose of study treatment + 1)/30.4375 (months).

For subjects with both of the following conditions fulfilled, the general censoring rules apply as presented in Table 3.

- Baseline tumor assessment
- At least one adequate tumor assessment after start of treatment

Table 3 General Censoring Rules for Progression-free Survival

| | | | Date of event / censoring | Censoring |
|--|---|-----|--|------------------|
| PD according to RECIST as assessed by the IERC | | | Date of PD | No |
| No PD | Death within 12 weeks after last tumor assessment or date of first study treatment (whichever is later) | Yes | Date of death | No |
| | | No | Date of last adequate tumor assessment | Yes |

IERC=Independent Endpoint Review Committee, PD=progressive disease.

For subjects with no tumor assessment at baseline or no tumor response assessment post-baseline, the special censoring rules as presented in Table 4, which overrule the general censoring rules, apply.

Table 4 Special Case Censoring Rules for Progression-free Survival

| | | | Date of event / censoring | Censoring |
|--|---|-----|----------------------------------|------------------|
| No tumor assessment at Baseline | Death within 12 weeks after first study treatment | Yes | Date of death | No |
| | | No | Date of first study treatment | Yes |
| No tumor response assessment post Baseline | Death within 12 weeks after first study treatment | Yes | Date of death | No |
| | | No | Date of first study treatment | Yes |

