16.6 Human Anti-human Antibody (HAHA)

Subjects will be categorized as either never positive or ever positive (a positive result at any time point, including baseline). Listings of all individual HAHA results from ever positive subjects will be prepared by time point.

Subjects with a positive HAHA result prior to treatment with Avelumab will be characterized as pre-existing. If the titer increases ≥ 8 fold while on Avelumab treatment, they will be additionally characterized as treatment-boosted. The summary table will include the total pre-existing incidence as well as the treatment-boosted incidence.

Subjects not positive prior to treatment with Avelumab and with at least one positive result in the HAHA assay will be characterized as treatment-emergent and further characterized for persistence of antibody response. Subjects will be categorized as transient positive (time between first and last positive result < 16 weeks apart and a negative result at the most recent visit) or persistent positive (time between first and last positive result ≥ 16 weeks apart or a positive evaluation at the most recent visit). The summary table will include the total treatment-emergent incidence as well as the persistent and transient incidence. Table 6 below summarized the criteria of different HAHA result categories.

Table 6 Subjects Characterized based on HAHA Results

| Category | Definition | Subjects at Risk (Denominator for Incidence) |
|---------------------|---|---|
| Never positive | No positive results at any time point | Number of subjects with at least one valid result at any time point |
| Ever positive | At least one positive result at any time point | Number of subjects with at least one valid result at any timepoint |
| Pre-existing | A positive HAHA result prior to treatment with avelumab | Number of subjects with valid baseline result |
| Treatment boosted | A positive HAHA result prior to treatment with avelumab and the titer $\geq 8 \times$ baseline titer while on avelumab treatment | Number of subjects with valid baseline and at least one valid post-baseline result |
| Treatment emergent | Not positive prior to treatment with avelumab and with at least one positive post-baseline result | Number of subjects with at least one valid post-baseline result and without positive baseline results (including missing, NR) |

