| Transient positive | If treatment emergent subjects have (a single positive evaluation, or duration between first and last positive result < 16 weeks) and last assessment not positive. | Number of subjects with at least one valid post-baseline result and without positive baseline results (including missing, NR) |
| Persistent positive | If treatment emergent subjects have duration between first and last positive result ≥ 16 weeks or a positive evaluation at the last assessment | Number of subjects with at least one valid post-baseline result and without positive baseline results (including missing, NR) |

If data permit (at least 5 ever positive or treatment emergent), subanalyses of immunogenicity responses on safety (TEAEs, TE irAEs, SAE, IRRs) and efficacy (PFS) will be performed using summary statistics for qualitative comparison only. This analysis will be conducted both by comparing ever positive versus never positive and by comparing treatment-emergent versus the rest of the subjects.

CCI

CCI

17 Safety Evaluation

Analysis sets: Safety analysis set

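### Part A compares PFS by antibody status taken from the whole of follow-up, which biases PFS in favour of antibody-positive subjects and can mask harm

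*SAP*

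**What the plan says.** Part A SAP, Section 16.6, sets the groups: "Subjects will be categorized as either never positive or ever positive (a positive result at any time point, including baseline". Its Table 6 defines a treatment-emergent subject as "Not positive prior to treatment with avelumab and with at least one positive post-baseline result". Both labels use all available samples. The section then plans subanalyses of safety and of PFS by these groups, on the condition "If data permit (at least 5 ever positive or treatment emergent". It plans two contrasts: "This analysis will be conducted both by comparing ever positive versus never positive and by comparing treatment-emergent versus the rest of the subjects". The results are to be summarised descriptively, without a test or a hazard ratio. Section 11 of the same SAP declares everything other than the primary test exploratory.

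PFS in Section 16.2.2 is the "time from first administration of trial treatment until first observation of PD or death", with death counted only inside a 12-week window.

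Protocol Section 7.6.3 schedules Part A antibody samples at baseline, then "within 2 hours before infusion on Days 15, 29, 43 (every 2 weeks) and then every 6 weeks thereafter while on treatment". One more sample is due when treatment has ended, at the End-of-Treatment visit. The Part A schedule in Appendix I also lets leftover serum from the 10-week safety visit be tested. Protocol Section 5.5.1 adds: "Subjects may continue avelumab treatment beyond radiological disease progression in the absence of significant clinical deterioration". A first positive sample can therefore fall after the PFS event.

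The visible text of Section 16.6 mentions no landmark, time-dependent status or other correction.

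**The concern.** The groups are formed with information that becomes available only after the PFS clock has started. Someone who progresses and stops treatment early gives few samples and is likely to be labelled negative. Someone who stays on treatment gives many and has more chances to be labelled positive. A longer PFS among positives can therefore arise with no antibody effect at all.

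The direction of the bias matters. The natural question for such a table is whether subjects with antibodies do worse, and the grouping pushes towards the answer that they do not. Section 5 of the SAP says that its planned analyses will go into regulatory submissions, so a falsely reassuring table could be read by people who rely on it.

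**Working it through.** The documents state no figure for this comparison, so there is nothing to reproduce. The check has three steps.

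**1. The mechanism in closed form.** Assume exponential PFS with median m and no antibody effect. For a subject still progression-free d days after first dose, median PFS from first dose is d + m. Take m = 90 days (assumed) and three Part A sampling days, the last being 43 + 42 = 85:

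- first positive at Day 15: 14 + 90 = 104 days
- first positive at Day 43: 42 + 90 = 132 days
- first positive at Day 85: 84 + 90 = 174 days

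A subject positive at baseline has d = 0 and gains nothing. A subject first positive after progression need not have been progression-free up to that sample, which weakens the effect.

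**2. Large simulations with no true effect** (400,000 subjects, exponential PFS, Part A sampling days). The measure is the event-rate ratio, (events / person-time in positives) ÷ (events / person-time in the comparator), with person-time from first dose. A value of 1 means no bias. PFS and seroconversion rates are assumptions.

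| Scenario | Ratio |
|---|---|
| Everyone at constant seroconversion risk, detected only before PD (16–29% positive) | 0.40–0.43 |
| Same, plus End-of-Treatment sample and 42 days of treatment after PD | 0.46–0.55 |
| Same, plus 5% positive at baseline (90-day median PFS) | 0.59 ever vs never; 0.56 treatment-emergent vs rest |
| 20% can convert, median onset 60 days, no End-of-Treatment sample | 0.63–0.73 |
| Same, plus End-of-Treatment sample | 0.77–0.83 |
| Same, plus 6 weeks of sampling after PD | 0.86–0.89 |
| Same, plus 5% positive at baseline | 0.88–0.92 |
| 10% can convert, median onset 30 days, all these features | 0.95–0.98 |

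In the first family of scenarios a Week 13 landmark was also run, and it returned 0.99–1.01.

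**3. Trials of the actual size** (88 subjects, the Part A enrolment in SAP Section 7). Ever versus never positive, with an End-of-Treatment sample. Runs with fewer than 5 subjects in either group were dropped. The rows below assume a median PFS of 180 days. HR is the true hazard ratio after a positive result.

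| Baseline positive | Later converters | Median onset | Ratio, HR 1 | Positives have longer median, HR 1 | Ratio, HR 2 | Positives have longer median, HR 2 |
|---|---|---|---|---|---|---|
| 0% | 30% | 90 days | 0.69 | 91.1% | 1.12 | 57.4% |
| 0% | 30% | 30 days | 0.88 | 69.9% | 1.57 | 11.9% |
| 2% | 10% | 90 days | 0.78 | 70.9% | 1.33 | 30.5% |
| 5% | 5% | 90 days | 0.88 | 57.4% | 1.66 | 15.4% |
| 5% | 5% | 30 days | 0.96 | 50.0% | 1.91 | 9.3% |
| 10% | 2% | 30 days | 1.00 | 47.9% | 1.99 | 5.9% |

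Across all settings run (median PFS 60, 90 or 180 days), the no-effect ratio lay between 0.67 and 1.03. Positives had the longer median in 47% to 92% of no-effect trials. With a true hazard ratio of 2 they still had it in 6% to 72%. In the first row a doubled hazard appears as a ratio of 1.12, so most of the harm is hidden.

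**The case against.** The strongest reply is that little rests on this table. It is conditional on at least 5 positives, purely descriptive and exploratory. The stated immunogenicity objective is to evaluate antibodies and relate them to exposure, not to show whether they shorten PFS. The Part B SAP plans listings and line plots for ever-positive subjects and shows no such group comparison of PFS in its visible text. All of that stands, and it limits the consequence. It does not remove the bias: leaving out a test removes the p-value, while the two curves or medians stay distorted.

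A reader might infer more, namely that positives are bound to show longer PFS. The documents do not support that. The ever-positive group includes baseline positives, who carry no immortal time, and samples can turn positive at End-of-Treatment or after progression. Chance in small groups, or a real harmful effect, can also reverse the picture.

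A reader might also take an extreme figure as the size. A model that detects antibodies only before progression, with 18–31% ever positive, gives apparent hazard ratios of 0.29 to 0.38. That model omits sampling features that the protocol contains, and the SAP plans no hazard ratio here.

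A fair practical objection is that a late landmark may leave too few positives. That also stands, and it argues for an early landmark or time-dependent status.

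**Conclusion.** The point holds as a bias of known direction and unknown size. Both planned PFS contrasts favour antibody-positive subjects and can mask a harmful effect. With no true effect, the apparent event-rate ratio is about 0.4 to 1.0. Low values need slow, continuing seroconversion; values near 1 arise when positives are present at baseline, appear early, or are picked up after progression or at End-of-Treatment. The treatment-emergent contrast is the more affected, because every positive in it is post-baseline and baseline positives sit in the comparator. In the one scenario where both were computed the difference was modest (0.56 against 0.59).

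These figures rest on exponential PFS and on assumed PFS and seroconversion rates. No primary or confirmatory conclusion depends on the comparison. It is a cheap improvement, not a threat to the trial.

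**What to change.** For PFS only, replace the two contrasts in Section 16.6 with one of the following:

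- **Time-dependent status.** A subject counts as negative until the first positive sample and as positive afterwards. This keeps everyone in the analysis.
- **An early landmark.** Classify by samples up to, for example, Day 43, and measure PFS from that day in subjects still progression-free. Day 43 is also the first scheduled tumour assessment, so state how progression found at that visit is handled.

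In either case show baseline-positive subjects as a separate group. Leave the incidence tables unchanged.

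No new data are needed. With a landmark, subjects who progress earlier leave the comparison, later converters count as negative, and few positives may remain. If median PFS were 3 months (3 × 30.4375 = 91.3 days, assumed, exponential), the share still progression-free would be 2^(−42/91.3) = 0.73 at Day 43, or about 64 of 88 subjects. At Week 13 it would be 2^(−84/91.3) = 0.53, or about 47. That is why the earlier landmark, or time-dependent status, is preferable.

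Protocol Section 10.6.2 shows that Part A results have already been published. If the tables already exist in the planned form, the minimum is a footnote saying that the grouping uses post-baseline information and favours positives.

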17.1 Adverse Events

Treatment emergent adverse events (TEAEs) are those events with onset dates occurring during the on-treatment period or if the worsening of an event is during the on-treatment period.

All analyses described in Section 17.1 will be based on TEAEs (started during the on-treatment period) if not otherwise specified. The AE listings will include all AEs (whether treatment-emergent or not). A separate listing including AEs started after the on-treatment period will also be provided.

- **Related Adverse Events:** adverse events with relationship to study treatment (as recorded on the AE eCRF page, Relationship with study treatment = Related) reported by the

investigator and those of unknown relationship (i.e. no answer to the question “Relationship with study treatment”).

- **Serious Adverse Events (SAE):** serious adverse events (as recorded on the AE eCRF page, Serious Adverse Event = Yes).
- **Adverse Events Leading to Treatment Discontinuation:** adverse events leading to permanent discontinuation of study treatment (as recorded on the AE eCRF page, Action taken with study treatment = Drug withdrawn).
- **Adverse Events Leading to Death:** adverse event leading to death (as recorded on the AE eCRF page, Outcome = Fatal, as well as AEs of Grade 5).
- **Infusion Related Reaction:** IRRs (as identified according to a pre-specified search list of MedDRA PTs, documented in a version-controlled repository maintained by the Sponsor and finalized for analysis of the current study data prior to DB lock) with onset on study drug dosing date (not prior to infusion of study drug) or the day following study drug infusion.
- **Immune Related Adverse Events (irAE):** irAEs are identified according to a pre-specified search list of MedDRA PTs, documented in a version-controlled repository maintained by the Sponsor and finalized for analysis prior to DB lock.

Unless otherwise stated adverse events will be displayed in terms of frequency tables: PT and primary SOC in alphabetical order. If an adverse event is reported for a given subject more than once during treatment, the worst severity and the worst relationship to trial treatment will be tabulated. Each subject will be counted only once within each PT or SOC and recording period. If a subject experiences more than one AE within a PT or SOC for the same recording period, only the AE with the strongest relationship or the worst severity, as appropriate, will be included in the summaries of relationship and severity.

Adverse events related to trial treatment are those events with relationship missing, unknown or yes.

17.1.1 All Adverse Events

Adverse events will be summarized by worst severity (according to NCI-CTCAE version 4.0) per subject, using the latest version of MedDRA preferred term (PT) as event category and MedDRA primary system organ class (SOC) body term as Body System category.

In case a subject had events with missing and non-missing grades, the maximum of the non-missing grades will be displayed. No imputation of missing grades will be performed.

The following tables will be created:

- The overall summary of AEs table will include the following summaries:
 - TEAEs
 - TEAEs, grade ≥ 3

- Related TEAEs
- Related TEAEs, grade ≥ 3
- TEAEs leading to permanent treatment discontinuation
- Related TEAEs leading to permanent treatment discontinuation
- Serious TEAEs
- Related serious TEAEs
- TEAEs leading to death
- Related TEAEs leading to death
- Treatment emergent irAEs
- Related treatment emergent irAEs
- Treatment emergent IRRs
- Related treatment emergent IRRs
- TEAEs by SOC and PT and worst grade
- Related TEAEs by SOC and PT and worst grade
- TEAEs leading to death by SOC and PT
- Related TEAEs leading to death by SOC and PT
- TEAEs by SOC and PT: displaying in separate columns the All TEAEs / Related TEAEs / Grade ≥ 3 TEAEs / Related Grade ≥ 3 TEAEs
- TEAEs excluding, SAEs with frequency $\geq 5\%$ by SOC and PT

A listing of AEs including all relevant information will be provided. In addition, a listing of non-TEAEs will also be provided.

17.1.2 Adverse Events Leading to Treatment Discontinuation

The following overall frequency tables will be prepared for the adverse event actions that lead to treatment discontinuation:

- AEs leading to permanent treatment discontinuation by SOC and PT
- Related AEs leading to permanent treatment discontinuation by SOC and PT

The listing of AEs leading to permanent treatment discontinuation will also be provided with the relevant information.

17.2 Deaths, Other Serious Adverse Events, and Other Significant Adverse Events

17.2.1 Deaths

All deaths, deaths within 30 days after last dose of study drug, death within 60 days after first dose as well as the primary reason for death, will be tabulated based on information from the “Report of Subject Death” and “Survival Follow-Up” CRFs.

- Number of Deaths
- Number of Deaths within 30 days after last dose of avelumab
- Number of Deaths within 60 days after first dose of avelumab
- Primary Reason of Death
 - Disease progression
 - Adverse event related to study treatment
 - Adverse event not related to study treatment
 - Other
 - Unknown

In addition, date and cause of death will be provided in individual subject data listing together with selected dosing information (date of first / last administration, number of infusions received overall) and will include the following information:

- AEs with fatal outcome (list preferred terms of AEs with outcome=Fatal, as well as AEs of Grade 5),
- flag for death within 30 days of last trial treatment
- flag for death within 60 days of first trial treatment

17.2.2 Serious Adverse Events

The following overall frequency tables will be prepared for serious adverse events (SAEs):

- Incidence of serious AEs by SOC and PT
- Incidence of related serious AEs by SOC and PT

The listings of SAEs will also be provided with the relevant information.

